15.5 Evaluation of Potential Effect of ADA on Bintrafusp alfa PK

Bintrafusp alfa concentration in serum will be descriptively summarized as described in Section 16.3 to evaluate the potential effect of ADA on PK.

16 Safety Evaluation

Analysis set: Safety Analysis Set

All safety description will be provided per dose level/cohort and overall (dose escalation overall, HCC overall, dose expansion overall (excluding HCC)).

16.1 Adverse Events

Treatment emergent adverse events (TEAEs) are those events with onset dates occurring during the on-treatment period for the first time, or if the worsening of an event is during the on-treatment period as defined in Section 9.7. Adverse events will be coded according to the most current version of MedDRA. Severity of AEs will be graded using the NCI-CTCAE v4.03 toxicity grading scale.

Changes in toxicity grade, seriousness or outcome of AEs are recorded as separate entries in the eCRF with associated end and start dates (start date equals end date of previous entry). Such entries reporting the same event in such immediately consecutive periods will be considered as one event in the analysis in case of a change in toxicity grade. These events will be kept as separate records in the database in order to maintain the full detailed history of the events. The start date of the initial record in the sequence is taken as start date of the entire event. Duration of the AE and the TEAE flag will be adjusted accordingly in the analysis.

All analyses described in this section will be based on TEAEs if not otherwise specified. The AE listings will include all AEs (whether treatment-emergent or not).

- **Related Adverse Events**: adverse events with relationship to study treatment (as recorded on the "Adverse Events Details" eCRF page, Relationship with MSB0011359C= Related) reported by the investigator and those of unknown relationship (i.e. no answer to the question "Relationship with MSB0011359C").
- **Serious Adverse Events (SAE)**: serious adverse events (as recorded on the "Adverse Events Details" eCRF page, Serious Adverse Event = Yes).
- Adverse Events leading to Treatment Discontinuation: adverse events leading to permanent discontinuation of study treatment (as recorded on the "Adverse Events Details" eCRF page, Action taken with MSB0011359C = Drug withdrawn).
- Adverse Events leading to Death: adverse event leading to death (as recorded on the "Adverse Events Details" eCRF page, Outcome = Fatal, as well as AEs of Grade 5).
- Adverse Events of Special Interest (AESI): adverse events of special interest (as identified according to a pre-specified search list of MedDRA Preferred Terms). Categories of AESI include:

- o Immune-Related Adverse Events (irAE)
- o Infusion-Related Reactions (IRR) including hypersensitivity
- O Skin AE possibly related to TGFβ inhibition
- o Anemia

Anemia events are those AEs belonging to the MedDRA HLT Anaemias NEC, HLT Anaemias haemolytic immune, HLT Anaemias haemolytic NEC or PT = Haemoglobin decreased.

• **Bleeding events** are those AEs belonging to the MedDRA SMQ Haemorrhage terms (excluding laboratory terms).

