8.5.5.1 Adverse Events

Adverse events will be coded according to the most current version of MedDRA. Severity of AEs will be graded using the NCI-CTCAE v4.03 toxicity grading scale.

The incidence TEAEs regardless of attribution and AEs defined as related to MSB0011359C will be summarized by Preferred Term and System Organ Class, and described in terms of intensity and relationship to MSB0011359C. Adverse events (serious and nonserious) will be considered TEAEs when emerging in the on-treatment period defined as the time from the first trial drug administration to the last drug administration date + 30 days or the earliest date of subsequent anticancer drug therapy minus 1 day, whichever occurs first, unless otherwise stated. AEs occurring after the last trial drug administration will always be classified as TEAE if it is considered trial drug-related by the Investigator. All premature terminations will be summarized by primary reason for treatment withdrawal.

1

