2.0	11APR2022	PPD	Cancellation of the final analysis after the database lock (IAP update performed after the CSR and CSR addendum deliveries in order to remove the protocol defined final data cut-off)

4 Purpose of the Integrated Analysis Plan

The purpose of this integrated analysis plan (IAP) is to document technical and detailed specifications for the analyses of data collected for bintrafusp alfa in MS200647-0008 study for CSR addendum.

Results of the analyses described in this IAP will be included in the Clinical Study Report (CSR) addendum with May 2020 cut-off. Additionally, the planned analyses identified in this IAP may be included in regulatory submissions or future manuscripts. Any post-hoc, or unplanned analyses performed to provide results for inclusion in the CSR addendum but not identified in this prospective IAP will be clearly identified in the CSR addendum.

The current analyses purpose is to provide additional data update using 15May2020 data cutoff. The analyses for the CSR were based on 24Aug2018 data cutoff. Since the last participant started on 24th August 2017, the following data will be unchanged from CSR and analyses will not be repeated:

- Demographics, medical history, others baseline characteristics and previous anticancer therapies
- Confirmed and unconfirmed Best Overall Response (BOR) by Investigator (BOR by Independent Review Committee (IRC) will be described as changes for gastric cohort have been observed) and related subgroup analysis

Following analysis will not be run using the new cutoff due to the exploratory nature of the non-safety endpoints:

- All irRECIST and mRECIST analysis
- Efficacy subgroup analysis for gastric cancer histology and PD-L1 expression in combined positive score
- Patient-reported Outcomes (PRO) analysis
- Cytokines analysis

But in the opposite, new analysis will be added and described in this IAP such as:

- Neutralizing antibody data (nAb) analysis
- ADA analysis (duration of response, time to onset, ADA titer analysis)
- Efficacy subgroup analysis by PD-L1 whole tumor and PD-L1 tumor microenvironment
- Bleeding events and anemia description
- COVID-19 analysis

5 Objectives and Endpoints

Refer to protocol version 7.

6 Overview of Planned Analyses

This IAP will address analyses used to support CSR addendum.

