9.7 Definition of On-treatment Period

On-treatment period is defined as the time from the first trial drug administration to the last trial drug administration date + 30 days OR the earliest date of subsequent anti-cancer therapy (including drugs, surgeries, radiotherapies) minus 1 day, whichever occurs first, unless otherwise stated.

For immune-related AEs as listed in Section 16.1.3.2, an expanded on-treatment period will be used as a default for any analysis:

Time from the first study intervention to the last study intervention date + 90 days, death OR to the earliest date of subsequent anticancer therapy minus 1 day, whichever occurs first, unless otherwise stated.

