16.2.3.2 Immune-Related Adverse Events

Immune-related adverse events (irAEs) will be identified programmatically. AEs which satisfy all of the following criteria will be flagged as immune-related:

- 1) The AE preferred term matches a preferred term on the list of pre-selected MedDRA terms.
- 2) The AE onset or worsening occurs after the first study drug administration and no more than 90 days after last dose, death or the earliest date of subsequent anticancer therapy minus 1 day, whichever occurs first.
- 3) On the AE eCRF page, the question "Were Corticosteroids, Immunosuppresants, or hormonal therapy (e.g. Thyroid) applied?" has the answer "Yes" selected.
- 4) On the imAE eCRF page, either:
 - a. The question "Does any of the following provide a clear etiology for the event?" has the answer "No" selected, indicating that the AE is not attributable to underlying cancer disease/PD, prior or concomitant medications/procedures, nor another medical condition such as an infection or pre-existing disease.

OR

b. The imAE eCRF indicates that a biopsy was performed and the question "Is the histopathology/biopsy consistent with an immune-mediated event?" has the answer "Yes" selected.

In the case that criteria (1) through (3) are met, and entries for condition (4) are missing, the following rules will be applied:

- If the answer to "Does any of the following provide a clear etiology for the event?" (4a) is missing, the event will be considered as irAE (irrespective of biopsy results).
- If the answer to "Is the histopathology/biopsy consistent with an immune-mediated event?" (4b) is missing, or if no biopsy was performed, and condition (4a) is not satisfied (i.e. "Yes" is selected as the answer to the question "Does any of the following provide a clear etiology for the event?"), the event will be considered as a non-irAE.

PTs will be compiled into categories: Immune-mediated rash, Immune-mediated colitis, Immune-mediated pneumonitis, Immune-related hepatitis, Immune-related nephritis and renal

dysfunction, Immune-mediated endocrinopathies (Adrenal insufficiency, Hypogonadism, Pituitary dysfunction, Type 1 Diabetes Mellitus, Thyroid disorders), Other immune-related adverse events (GVHD, Myasthenic syndrome, Myocarditis, Myositis, Neurologic events, Other, Pancreatitis, Uveitis, Vasculitis).

The overall summary of immune-related AEs (irTEAE) will include the following categories:

- Any irAEs
- irAEs by the worst grade
- Related irAEs

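### The SAP for the CSR addendum drops, without declaring it, the protocol rule that related AEs after the last dose are always TEAEs, so some late related events leave the related-TEAE tables

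*SAP*

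**What the plan says.** **Protocol 8.5.5.1.** TEAEs are events that emerge between first dose and last dose + 30 days. The period ends sooner at "the earliest date of subsequent anticancer drug therapy minus 1 day, whichever occurs first, unless otherwise stated". A separate sentence follows: "AEs occurring after the last trial drug administration will always be classified as TEAE if it is considered trial drug-related by the Investigator". It has no end date and no qualifier.

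**SAP 16.1 and 9.7.** The definition is "Treatment emergent adverse events (TEAEs) are those events with onset dates occurring during the on-treatment period for the first time", or worsening within the period. The period also ends 30 days after the last dose, but the cut is wider: "the earliest date of subsequent anti-cancer therapy (including drugs, surgeries, radiotherapies) minus 1 day, whichever occurs first". For immune-related AEs "an expanded on-treatment period will be used as a default for any analysis", namely 90 days. Criterion 2 of SAP 16.2.3.2 sets the same limit: "no more than 90 days after last dose, death or the earliest date of subsequent anticancer therapy minus 1 day, whichever occurs first". No SAP section carries the protocol's rule for related events.

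**Which outputs follow it.** SAP 16.1 states: "All analyses described in this section will be based on TEAEs if not otherwise specified". Listings include all AEs.

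**Declared changes.** SAP Section 4 lists what is not repeated and then, after "But in the opposite, new analysis will be added and described in this IAP such as", what is new. Section 7 reports only the cancelled final analysis, and 7.1 only COVID-19 outputs. None mentions the TEAE definition. Section 5 refers to protocol version 7 for objectives and endpoints.

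**The concern.** After the End-of-Treatment visit the protocol collects only AEs that the investigator attributes to the drug. Those are the events its extra TEAE sentence was written to count. Under the SAP they are still collected but are not tabulated as TEAEs.

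This matters because related AEs are a protocol primary endpoint (8.3.1), and 8.5.2.1 plans to tabulate related TEAEs by worst severity at each dose level. A reader of the addendum who assumes the protocol definition would take the related-TEAE rates as complete. Section 4 also allows these analyses to enter submissions or manuscripts.

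**Working it through.** The plan gives no figure to reproduce. The check compares the texts and counts days after the last dose.

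**1. Are such events collected?** Yes. Protocol 7.4.1.3 records all AEs to the End-of-Treatment visit (28 ± 5 days, so day E = 23 to 33). It then records related AEs to the Safety Follow-up visit (10 ± 2 weeks, so day F = 56 to 84, nominally 70). Related SAEs are reportable without limit.

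**2. Group (a): related, outside the SAP irAE definition, no new therapy.** The SAP window ends on day 30.
- Uncounted days = F − 30: 56 − 30 = 26, 70 − 30 = 40, 84 − 30 = 54.
- Of these, days on which only related AEs are collected = F − max(30, E): minimum 56 − 33 = 23, maximum 84 − 30 = 54.
- Related SAEs have no upper limit.
- An event that meets the irAE definition is counted to day 90, which is beyond day 84. Without new therapy, only related SAEs after day 90 are then lost.

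**3. Group (b): related, starting on or after new anticancer therapy.** If therapy starts on day d, the window ends on day d − 1 and the uncounted days are F − d + 1. The documents do not give d, so two values are assumed.
- d = 15: 56 − 15 + 1 = 42 to 84 − 15 + 1 = 70.
- d = 30: 56 − 30 + 1 = 27 to 84 − 30 + 1 = 55.

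The irAE outputs do not recover this group, because the 90-day window stops at new therapy too.

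**4. Which tables change?**
- *Affected:* the related, related Grade ≥3 and related serious TEAE tables (SAP 16.1.1, 16.2.2) and the skin TEAE tables (16.2.3.3).
- *Affected if TEAE-based:* anemia and bleeding. Their overview lines in 16.1.1 are TEAE lines, but 16.2.3.4 and 16.2.4 do not say, and the default sentence sits in 16.1.
- *Practically unaffected:* discontinuation and drug-interruption tables, since an event starting this late can hardly change dosing, and infusion-related reactions, whose onset is on the infusion day or the day after.
- *Unaffected:* DLT and MTD results, which use a 21-day window from first dose (Protocol 5.1.3.3).

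**5. Direction.** Hold fixed the definition of related and the handling of worsening. The SAP's related TEAEs are then a subset of the protocol's. The number of subjects with any related, related Grade ≥3 or related serious TEAE is equal or lower. Cells for lower worst grades can move either way, because a subject whose late Grade 3 event is dropped may reappear at a lower grade.

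**6. A separate conflict on the same flag.** SAP 16.1 merges consecutive records of one AE on any grade change. SAP 16.1.1 merges them only on improvement. Take an event that starts on treatment at Grade 1 and worsens to Grade 3 after the window. Under 16.1 it is one Grade 3 TEAE. Under 16.1.1 it is a Grade 1 TEAE plus a Grade 3 record outside the window.

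**The case against.** **The SAP governs only the addendum.** This stands. The main CSR used the 24 August 2018 cut-off, and its plan is not among the documents. A reader might infer that the trial's primary safety analysis was built on the wrong definition. The documents do not support that, because how the main CSR tables were built cannot be judged.

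**The events are not hidden.** This stands in part. The AE listing flags onset or worsening after the on-treatment period (SAP 16.1.1). SAP 16.2.3.2 adds a separate listing of irAEs that start after the period. Related SAEs, related life-threatening cases and related Grade >3 AESIs receive narratives whenever they occur (16.3), and all deaths are tabulated (16.2.1). None of this restores a frequency. A late related Grade 3 event that is not serious and falls outside the irAE definition appears only in a listing, unless the case-by-case narrative item picks it up.

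**The direction is not certain.** This stands unless the two conditions in the working hold. SAP 16.1 counts worsening on treatment, whereas Protocol 8.5.5.1 speaks only of events that emerge. If that means onset alone, the SAP can count some events that the protocol does not.

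**The effect may be trivial.** This cannot be settled. A reader might infer a large effect from the small dose levels, since one subject in three is 1/3 = 33.3 points. That is the step size of any rate with three subjects, and it says nothing about how many events were dropped.

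**The surgery and radiotherapy cut is allowed.** Arguably so, because the protocol's window carries an unless-otherwise-stated clause. That clause qualifies the window and not the sentence on related events that follows it.

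**Conclusion.** The omission is real and undeclared. It should be fixed, but its reach is limited. In the addendum, two groups of related AEs leave the related-TEAE frequency tables: those outside the irAE definition that start after day 30, and any, irAEs included, that start on or after new anticancer therapy. For the first group the uncounted period is 26 to 54 days, with no limit for related SAEs. The second depends on when new therapy starts, which the documents do not give. The number of events is unknown.

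The conclusion rests on the SAP having been programmed as written and on irAEs keeping their 90-day window in every TEAE table, which is the reading most favourable to the SAP. No MTD conclusion depends on these counts, and SAP 9.10 plans no statistical test of the study endpoints. The merging conflict is a distinct defect that can change TEAE flags and worst grades.

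**What to change.** - **Declare it.** State in SAP Section 7 that the addendum TEAE tables did not apply the protocol's rule for related events after the last dose, and that the window is also cut at surgery and radiotherapy. Rewriting the definition without rerunning the tables would make the SAP contradict the addendum approved on 25 March 2021.
- **Supplement it.** Add one table by dose level/cohort of investigator-related AEs (any grade, Grade ≥3, serious) under the protocol rule, regardless of the on-treatment window.
- **Later outputs.** Apply the protocol rule in 9.7 and 16.1 to any TEAE tables produced later for submissions or manuscripts.
- **Merging.** Replace the two sentences in 16.1 and 16.1.1 with one rule that matches what was programmed.

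The cost is small programming work, since the after-period flag already exists for the listing, plus one table added to an approved report. Related-AE rates may come out slightly higher.

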7.4.1.3 Definition of the Adverse Event Reporting Period

The AE reporting period for safety surveillance begins when the subject is included into the trial (date and time of first signature of informed consent) and continues through the trial's End-of-Treatment visit, defined as 28 days (± 5 days) after last trial drug administration. After the

CONFIDENTIAL INFORMATION

End-of-Treatment visit, only AEs that are deemed attributable to trial drug by the Investigator should be documented until the Safety Follow-up visit, defined as 10 weeks (± 2 weeks) after the last trial drug administration.

Any SAE assessed as related to MSB0011359C must be reported whenever it occurs, irrespective of the time elapsed since the last administration of MSB0011359C.

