8.3 Endpoints

8.3.1 Primary Endpoints

The primary endpoints for the dose escalation part of the trial are:

- Occurrence of DLTs during the first 3 weeks (21 days) of treatment in the dose escalation part.
- Number, severity, and duration of treatment-emergent AEs (TEAEs) according to the NCI-CTCAE v4.03.
- Number, severity and duration of treatment-related AEs for all dose groups/indications according to CTCAE v4.03.

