16.1.1 All Adverse Events

Adverse events will be summarized by worst severity (according to NCI-CTCAE version 4.03) per patient, using the latest version of MedDRA preferred term (PT) as event category and MedDRA primary system organ class (SOC) body term as Body System category.

Each patient will be counted only once within each PT or SOC. If a participant experience more than on AE within a PT or SOC for the same recording period, only the AE with the strongest relationship or the worst severity, as appropriate, will be included in the summaries of relationship and severity.

Changes in toxicity grade, seriousness or outcome of AEs are recorded as separate entries in the eCRF with associated end and start dates (start date equals end date of previous entry). Such entries reporting the same event in such immediately consecutive periods will be considered as one event in the analysis in case of an improvement in toxicity grade. These events will be kept as separate records in the database in order to maintain the full detailed history of the event. The start date of the initial record in the sequence is taken as start date of the event of entire event. Duration of the AE and the TEAE flag will be adjusted accordingly in the analysis. Of note if a record has an outcome resolved (with or without sequelae), this can't be an 'intermediate' record.

Unless otherwise stated adverse events will be displayed in terms of frequency tables: PT and primary SOC in alphabetical order.

- If an adverse event is reported for a given participant more than once during treatment, the worst severity and the worst relationship to trial treatment will be tabulated. In case a participant had events with missing and non-missing grades, the maximum of the non-missing grades will be displayed.
- The overall summary of AEs table will include the frequency (number and percentage) of patients with each of the following:
 - TEAEs
 - Related TEAEs
 - Serious TEAEs

- Related Serious TEAEs
- TEAEs, Grade ≥ 3
- Related TEAEs, Grade ≥3
- TEAEs leading to death
- Related TEAEs leading to death
- TEAEs and related TEAE of special interest:
 - o Infusion-related reactions (IRRs)
 - o Immune-related AEs (irAEs)
 - Potential TGF-β-mediated skin AEs
 - o Anemia
- TEAE, bleeding events
- Related TEAEs bleeding events
- TEAEs leading to study termination
- Related TEAEs leading to study termination

The following incidences will be summarized by SOC and PT

- TEAEs
- TEAEs by worst grade

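### SAP 16.1 and 16.1.1 join consecutive AE records by different rules, so event number, onset and duration (and, for some AEs, the TEAE flag or grade) are not fixed

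*SAP*

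**What the plan says.** SAP 16.1 and 16.1.1 both explain that changes in grade, seriousness or outcome are entered as separate eCRF records, each starting on the date the previous one ended. Both then say when to treat such a chain as one event:

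- SAP 16.1: the records "will be considered as one event in the analysis in case of a change in toxicity grade".
- SAP 16.1.1: the records "will be considered as one event in the analysis in case of an improvement in toxicity grade".

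The consequences are the same in both sections. In the words of 16.1, "The start date of the initial record in the sequence is taken as start date of the entire event", and "Duration of the AE and the TEAE flag will be adjusted accordingly in the analysis". SAP 16.1.1 adds only that a record with a resolved outcome cannot be an intermediate link.

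The opening sentence of SAP 16.1 makes an AE treatment-emergent if its first onset is on treatment, "or if the worsening of an event is during the on-treatment period as defined in Section 9.7". The definition in Protocol 8.5.5.1 has no worsening limb: AEs "will be considered TEAEs when emerging in the on-treatment period". Protocol 7.4.1.3 says the reporting period "begins when the subject is included into the trial (date and time of first signature of informed consent", so AE records can start before the first dose.

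Protocol 8.3.1 lists "Number, severity, and duration of treatment-emergent AEs (TEAEs) according to the NCI-CTCAE v4.03" among the primary endpoints of the dose escalation part, and Protocol 8.5.2.1 plans their number, worst severity and duration by dose level.

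**The concern.** A change covers worsening and improvement; an improvement covers only one direction. The two sections therefore treat every worsening differently, and no text ranks them. A programmer who follows 16.1 and one who follows 16.1.1 build different AE datasets from the same records.

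The any-change rule also sits badly with the definition in its own section. On-treatment worsening is meant to make an AE treatment-emergent, yet joining the worsened record to an earlier one moves its onset back, possibly to before the first dose. At stake are the number, onset and duration of events and, for AEs that cross the first dose or the end of the on-treatment period, the TEAE flag or worst grade.

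**Working it through.** The plan gives no figure to reproduce. I applied both rules to four invented record sequences.

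**Inputs.** Duration is stop minus start plus 1 (SAP 9.4). There is no day 0 (SAP 9.3), so a span crossing the first dose is the pre-dose days plus the days from day 1. The on-treatment period runs to 30 days after the last dose, or to the day before subsequent anticancer therapy if earlier (SAP 9.7). I assume a last dose on day 100 and no earlier therapy, so the period is days 1 to 130.

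**1. AE wholly on treatment:** Grade 1 from day 5, Grade 3 from day 12, Grade 1 from day 20 to day 30.
- 16.1: one event, 30 − 5 + 1 = 26 days.
- 16.1.1: the worsening is not joined but the later improvement is. Two events: 12 − 5 + 1 = 8 days and 30 − 12 + 1 = 19 days. (They share day 12 because each record starts on the day the last one ends.)
- Worst grade is 3 and the patient counts once under both rules.

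**2. AE arising after consent and before first dose:** Grade 1 from day −10, Grade 3 from day 21 to day 35.
- 16.1: one event from day −10, lasting 10 + 35 = 45 days. If the worsening limb governs, this is one Grade 3 TEAE of 45 days. If the flag is re-derived from the joined start date, there is no TEAE.
- 16.1.1: the Grade 3 record is its own event and a TEAE on either reading of the flag, lasting 35 − 21 + 1 = 15 days.
- The 30-day gap (45 − 15) is 10 pre-dose days plus days 1 to 20 at Grade 1.

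**3. AE worsening after the on-treatment period:** Grade 1 from day 120, Grade 3 from day 140 to day 150.
- 16.1: one TEAE, worst Grade 3, 150 − 120 + 1 = 31 days.
- 16.1.1: one Grade 1 TEAE, 140 − 120 + 1 = 21 days. The Grade 3 record falls outside the period.

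**4. Control, improvement only:** Grade 3 from day −5, Grade 1 from day 10 to day 20. Both rules join the records, the start is before dosing and nothing worsens, so neither gives a TEAE.

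The rules diverge only when a grade rises. Number, onset and duration differ in sequence 1 whatever is decided about the flag.

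**The case against.** The wording conflict is hard to dispute, but its reach can be.

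- **Flag loss.** A reader might infer that 16.1 strips the TEAE flag from AEs that worsen on treatment. The SAP does not say so. It says the flag is adjusted, without saying how, and the same section counts on-treatment worsening as treatment-emergent. Read together, the joined event can keep its flag. This stands: loss is a possible reading only, and only for AEs that began before dosing. The longer duration in sequence 2 remains.
- **Entry-level anemia.** Hemoglobin of 9 g/dL is enough for entry, so anemia that worsens may seem the obvious victim. Under Protocol 7.4.1.1.3, conditions present at the initial visit are not AEs unless they worsen, so such anemia usually has no earlier AE record to be joined to. Hemoglobin shifts are also tabulated separately (SAP 16.4.1). This stands.
- **Late worsening.** After the End-of-Treatment visit only drug-attributable AEs are documented (Protocol 7.4.1.3), and Protocol 8.5.5.1 always classes related AEs after the last dose as TEAEs, although the SAP does not repeat that. Immune-related AEs have a 90-day window (SAP 9.7). Sequence 3 therefore matters mainly for unrelated AEs: in the few days before that visit, after early subsequent therapy, or in serious events under follow-up.
- **Incidence tables.** SAP 16.1.1 counts each patient once per preferred term or system organ class at worst grade, so AEs wholly on treatment give the same incidence and grade. The SAP specifies no duration table; duration appears in listings. This stands, but Protocol 8.5.2.1 does plan duration as part of the primary analysis.
- **Timing.** This SAP serves the CSR addendum. The main CSR was approved before SAP version 1.0 was dated, and no final analysis will follow (SAP 3, 6.1). No effect on the main CSR can be shown.

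**Conclusion.** The concern holds in limited form. The two sections give incompatible joining rules with no order of precedence, and event number, onset and duration depend on which was used: 26 days as one event against 8 and 19 days as two, or 45 days against 15, in the examples. For an AE that newly arises between consent and first dose and then worsens on treatment, the 16.1 rule counts pre-dose days in the TEAE duration and leaves the flag open. For an AE not considered drug-related that worsens after the on-treatment period, it can raise the TEAE worst grade.

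The documents do not support the stronger inference that the primary safety incidence is wrong or that TEAEs have been lost. Incidence changes only if the flag is lost, and the DLT endpoint rests on events confirmed by the Safety Monitoring Committee (Protocol 5.1.3.3). The day counts come from invented sequences with an assumed last dose on day 100. How many AEs are affected cannot be derived from the documents. The point should be corrected because results under this SAP may still enter submissions or manuscripts (SAP 4).

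**What to change.** 1. In SAP 16.1, limit joining to an improvement in toxicity grade, as 16.1.1 already does. This is the version that agrees with the worsening limb of the TEAE definition.
2. Add one sentence: a record with a higher grade than the one before it starts a new event dated from the worsening, is a TEAE if that date lies in the on-treatment period, and has its duration counted from that date.
3. Confirm which rule was programmed for the CSR addendum. If it was the any-change rule, list the AEs whose joined chain crosses the first dose or the end of the on-treatment period.

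The text change is one word and one sentence, with the matching derivation in the AE analysis dataset. The check needs no new data, because SAP 16.1 keeps the separate records in the database.
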